## **Compensation**

Participants enrolled in the main study (RCT) will receive compensation of \$50 for completion of the Baseline and 3-month visits, and \$25 for the 1- and 2-month visits. Thus the maximum compensation for completing the main study is \$150. Compensation will be provided at the completion of each visit.

## **Data Safety and Monitoring**

Study Monitor: The study physician will serve as a Study Monitor to review all laboratory results, abnormal test scores (MMSE and CESD), and adverse events for individual participants.

Data Safety and Monitoring Board (DSMB): This project is funded as a Pilot Study through the UF Claude D. Pepper Older Americans Independence Center (OAIC) grant (NIH P24 AG028740 ) and thus uses the OAIC Data Safety Monitoring Board (DSMB).

The DSMB is an established board which has reviewed all studies conducted within the UF OAIC during for the past seven years. This board meets semi-annually. Membership comprises (1) [name]., Chair, an epidemiologist who has been involved in research for many years; (2) [name]., a biostatistician who has been involved with many clinical trials; and (3) [name]., a physician who has been involved in the conduct of clinical research for many years. DSMB Reports will be provided to the UF IRB-01 with annual Continuing Review submissions.

## **7. Possible Discomforts and Risks:**

### **General Approach.**

All assessment visits will be conducted at a central location fully equipped with a semi-automated ECG and defibrillator.

All sessions are conducted by research staff trained to monitor potential adverse experiences and symptoms during the testing sessions. All personnel associated with the study have completed Basic Life Support (BLS) training and education on management of acute events including syncope, chest pain, acute dyspnea, focal neurological symptoms and abnormal vital signs. Contact numbers for emergency services are posted, and community EMS services will be activated if needed.

Participants will be instructed to talk with the investigators about any discomforts that occur during the study. If a participant reports an injury, chest pain, leg swelling, excessive shortness of breath, palpitations, or dizziness, he/she will be referred to medical attention (his/her doctor, or Emergency Department).

All research staff complete protection of human research subjects training required by the University of Florida institutional review board (IRB) and National Institutes of Health (NIH). This training includes education about the importance of maintaining confidentiality of personal health information.

**Specific Potential Risks.** Potential risks for this study are related to the following: (1) use of study product, (2) blood draw procedure, (3) blood pressure measurement procedure, (4) testing for depression and cognitive function; (5) the physical performance tests, and (6) potential loss of confidentiality related to study participation

1. Risks associated with curcumin. Curcumin and chemically-related “curcuminoids” are bioactive polyphenolic compounds extracted from turmeric. These compounds are used in large amounts in Eastern cooking (e.g., curry), as dietary supplements, and to treat inflammatory conditions in India for centuries. Findings over the past few decades indicate that curcumin has a broad range of biological properties, including anti-inflammatory and anti-oxidative properties,

directly relevant to human health. In recent clinical trials, doses ranging from 1000-2500 mg of curcumin per day have been found to be safe and well tolerated.

C3 Complex (Sabinsa Corporation, Piscataway NJ) was chosen for this study due to reproducibility of the curcuminoid content and the curcumin dose. and is currently commercially available as a nutraceutical “bio-protectant.”

Potential disease or drug interactions with curcumin have been suggested in animal studies and human case reports; however, the clinical implications of these findings are largely unknown.

- Curcumin may reduce levels of blood glucose and glycosylated hemoglobin (HbA1c), possibly through a PPAR-γ mechanism^43. Persons currently taking medication to lower blood glucose are excluded from participation.
- Turmeric has been reported to have antiplatelet effects, so that concurrent use of curcumin with anticoagulants or antiplatelet drugs could theoretically increase the risk of bleeding. Persons with bleeding disorders or persons taking anticoagulant medications or antiplatelet agents (other than aspirin 81 mg daily) are excluded from participation. Participants taking low dose aspirin are monitored for increased bruising or bleeding and study medication is discontinued should this occur.
- Turmeric has been reported to cause gall bladder contractions. Persons with cholelithiasis or other gall bladder or biliary tract disease are excluded from participation.
- Curcumin may chelate iron and reduce its absorption. Serum ferritin will be checked at screening. Persons with chronic gastrointestinal blood loss or iron deficiency (serum ferritin < 12 ng/mL, with or without anemia) are excluded from participation
- *In vitro* evidence suggests that curcumin can competitively inhibit binding of 3H-estradiol or β-galactosidase to estrogen receptors and thus, theoretically, may have mild estrogenic effects. Persons with a history of estrogen-sensitive conditions including breast, uterine, and ovarian cancers; endometriosis, and uterine fibroids are excluded from participation.
- *In vitro* and animal studies suggest that curcumin may suppress cytochrome P450 1A1 (CYP1A1), cytochrome P450 1A2 (CYP1A2) cytochrome P450 3A4 (CYP3A4), so theoretically curcumin could increase levels of drugs metabolized by these enzymes. These interactions have not been reported in humans. However, persons taking MAO inhibitors or cholinesterase inhibitors are excluded from participation.

Specific information on side effects observed in clinical trials is limited due to the small size of most studies, the patient populations (ages and diseases studied), different doses and composition of curcumin, and the efficacy focus of the clinical research. The most commonly reported side effects include upset stomach, nausea, dizziness, and diarrhea. In a recently published multi-center clinical trial comparing ibuprofen to curcumin extract in the treatment of osteoarthritis, curcumin extract was associated with fewer adverse events than ibuprofen in all complaints except loose stools, although differences were statistically significant only for abdominal pain/distension (see Table 3 below).

Table 3. Adverse Events	Ibuprofen 1200 mg (n = 182)	Curcumin extract 1500 mg/day (n = 187)	P-value
--------------------------------	-----------------------------------	--	---------

	Mean age 60.9 yr	Mean age 60.3 yr	
Number of patients with AE	65 (35.7%)	55 (29.7%)	0.222
Number of events	33 (18.1)	20 (10.8)	0.046*
Abdominal pain and/or distension	29 (15.9%)	21 (11.1%)	0.201
Dyspepsia	15 (8.2%)	9 (4.9%)	0.091
Nausea	16 (8.8%)	22 (11.9%)	0.324
Loose stools	2 (1.1%)	-	0.245
Melena	13 (7.1%)	7 (3.8%)	
Pitting edema			
Kuptmiratsakul V et al. Efficacy and safety of Curcuma domestica extracts compared with ibuprofen in patients with knee osteoarthritis: a multicenter study. Clinical Interventions in Aging 2014;9 451-458 (Reference 74)			

Monitoring for Adverse Events (AEs). An Adverse Event (AE) is any unfavorable and unintended sign (including an abnormal laboratory finding), symptom, or disease temporally associated with a study intervention that *may* or *may not* be related to the intervention. At monthly study visits, participants will be queried about specific AEs as above and instructed to report any additional adverse effects they experience related to the study coordinator or other member of the investigative team. Basic blood chemistry and CBC from each visit will be reviewed by the Safety Monitor (study physician).

Grading scales found in the National Cancer Institute (NCI) Common Terminology Criteria for Adverse Events (CTCAE) version 4.0 ([http://evs.nci.nih.gov/ftp1/CTCAE/CTCAE\\_4.03\\_2010-06-14\\_QuickReference\\_8.5x11.pdf](http://evs.nci.nih.gov/ftp1/CTCAE/CTCAE_4.03_2010-06-14_QuickReference_8.5x11.pdf)) will be utilized for AE reporting. All AEs will be reviewed by the Safety Monitor (study physician) upon ascertainment.

- Grade 1 adverse events are mild; asymptomatic or mild symptoms; clinical or diagnostic observations only; intervention not indicated
- Grade 2 adverse events are moderate; minimal, local, or noninvasive intervention indicated; limit age-appropriate instrumental ADLs (preparing meals, shopping for groceries or clothes, using the telephone, managing money, etc.)
- Grade 3 adverse events are severe or medically significant but not immediately life threatening; hospitalization or prolongation of hospitalization indicated disabling or limit self-care ADLs (bathing, dressing and undressing, feeding self, using the toilet, taking medications, and not bedridden)
- Grade 4 adverse events have life-threatening consequences, urgent intervention indicated
- Grade 5 adverse event are fatal, resulting in death.

Common Terminology Criteria for Adverse Events (CTCAE) (Version 4.0) are defined for gastrointestinal side effects reported with curcumin in Appendix A.

Study medication will be stopped for the following reasons:

- Moderate to severe adverse effect symptoms limiting participant continuation in the study (Grade 3 or 4 toxicity)
- Elevation in liver function tests to 2x upper limits of normal or increase in serum creatinine to 1.5x baseline value
- Decrease in hemoglobin of > 1 g/dL from previous visit
- Development of medical problems listed as exclusion criteria
- Need for medications listed as exclusion criteria

As curcumin is well-tolerated, no Grade 3 or 4 toxicities are expected and no dose modifications are planned for this study.

This study will have a Safety Monitor (study physician) for continuous monitoring of individual participant results, and aggregate data will be reviewed semiannually by the Claude D. Pepper OAIC DSMB (see above).

2. Risks associated with blood draw. Risks include discomfort with the puncture and the possibility of a small bruise at the puncture site. To avoid these risks, research staff are trained in proper phlebotomy techniques

3. Risks associated with blood pressure measurement. The risks of placing a blood pressure cuff on a participant's arms are that it may cause pinching or slight bruising. To avoid this risk, research staff are trained in procedures for measuring blood pressure

4. Risks associated with cognitive function tests. Participants may experience fatigue and feelings of frustration while completing the cognitive function tests. Participation also includes a risk of loss of confidentiality of personal health information. To minimize these risks, research staff are trained in the conduct of the cognitive function tests and certified by [name] or his designee before they work with study participants.

6. Risks associated with physical performance tests. The 400-meter test may be associated with the risk of falling or development of chest discomfort due to coronary ischemia or dyspnea due to heart failure or lung disease. Rarely, falling during the 400-meter walk test may result in a fracture. Similar to the six-minute walk test, completion of the SPPB may be associated with the risk of falling or development of chest discomfort due to coronary ischemia or dyspnea due to heart failure or lung disease. Rarely, falling during the SPPB test may result in a fracture.

To minimize these risks, research staff are trained in the conduct of all physical performance tests and certified by [name] or his designee before they work with study participants. Study staff are instructed not to perform these tests if they feel that testing is unsafe for an individual participant or if the participant is concerned about safety. If safety concerns are identified by either the study staff or the participant during the testing procedures, testing is halted and the participant is not allowed to complete the test. In either case, the participant is assessed to determine the need for medical intervention and the cause for concern is evaluated. All study staff are trained in activating the emergency response system at The University of Florida facility.

7. Risks associated with questionnaire administration. Sensitive information collected for this study includes lifestyle factors (e.g., alcohol use) and personal health information (PHI) and are used predominantly in screening for eligibility and safety. Participation includes a risk of loss of confidentiality of this information.

To minimize risk, questionnaire data are collected in secure spaces where the interview cannot be overheard. Participants are reminded that they can decline to answer questions that are uncomfortable or concerning. All research staff members complete annual HIPPA for Researchers training as required by UF.

Collected data are maintained in locked computer files and file cabinets to which only study investigators have access. Only study investigators and key research staff (i.e. data manager and study programmers) have access to the study forms or database. Participants are assigned a unique study identifier; individual names will be removed from the study database and only the unique study identifier used to distinguish participants in the database. Collected data will be used only for research purposes, and publications will not contain any individual identifiers.

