**Exclusion Criteria (Curcumin-related)**

- Diabetes mellitus currently taking medications to lower blood glucose (oral or by injection)
- Current use of anticoagulant or anti-platelet medications (aspirin 81 mg daily is allowed)
- Congenital or acquired bleeding disorders
- Cholelithiasis or other gall bladder or biliary tract disease
- Chronic gastrointestinal blood loss or iron deficiency (serum ferritin < 12 ng/mL, with or without anemia)
- History of estrogen-sensitive conditions including breast, uterine, and ovarian cancers; endometriosis; and uterine fibroids
- History of Tuberculosis (TB), HIV, Hepatitis B or C, or other disease potentially compromising immune function

- Current use of:
  - medications targeting immune or inflammatory function (e.g., sulfasalazine, systemic corticosteroids)
  - anabolic medications (e.g., growth hormone, testosterone)
  - monoamine oxidase inhibitors (e.g., phenelzine, selegiline, tranylcypromine)
  - anticholinesterase inhibitors (e.g., donepezil, rivastigmine, galantamine)

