### **Enrollment and Randomization**

24 eligible participants will be enrolled and randomized to allow for 6 participant failures or withdrawals

At the baseline visit, the Informed Consent document for the RCT will be reviewed with the potential participant and written consent obtained. Participants will undergo a battery of physical performance tests (400-meter walk; short physical performance battery, grip strength and endurance), formal tests of cognitive function, and a blood draw of about 60 ml (See Table 1). Quality of Life and pain will be assessed with the AM-PAC, the SF-36, and the Brief Pain Inventory (BPI). Self-report of physical activity and dietary fat intake will be obtained through brief questionnaires (RAPA and Block High Fat screen).

Participants will then be randomized to receive either curcumin (1000 mg/day; n = 15) or placebo (microcrystalline cellulose; n=15) for a three-month period. The study drug will be provided for the first month according to randomization.

Participants in both groups will be instructed to return to the research center every month for the duration of the three-month trial. At the monthly visits, compliance with the supplementation regimen for the previous month will be assessed by pill count and participants will be provided with another month's supply of study medication according to initial randomization. Participants will be queried about any adverse events they experienced since their previous visit and any medical history updates they may need to provide. Additionally, blood samples will be obtained (chemistry 15 panel and complete blood count) to ensure that no adverse changes have occurred since their previous visit.

To enhance retention and to ensure participant safety, participants will receive bi-weekly telephone calls throughout the intervention period to ascertain adverse events and express appreciation for participation.

Following the three month supplementation period (Month 3 visit), participants will complete a post-treatment assessment including the battery of physical performance tests (400-meter walk, short physical performance battery, grip strength and endurance); cognitive function tests; questionnaires for quality of life, pain symptoms, and physical activity; and a blood draw of approximately 60 ml (See Table 2).

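### The hemoglobin stop is measured only from the previous visit, so at Month 2 a participant can be up to 2.0 g/dL below Baseline without a mandatory stop

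*Combined protocol and SAP*

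**What the plan says.** Section 7 (Possible Discomforts and Risks) lists the reasons for stopping study medication. The hemoglobin entry is "Decrease in hemoglobin of > 1 g/dL from previous visit". The entry just above it uses a fixed reference: "increase in serum creatinine to 1.5x baseline value". No section limits the fall in hemoglobin from Baseline or sets a floor.

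Under Enrollment and Randomization, participants "return to the research center every month for the duration of the three-month trial", and the monthly bloods are taken "to ensure that no adverse changes have occurred since their previous visit". Each monthly visit before the last also provides the next month's supply.

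Other provisions bear on a slow fall:

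- The study physician reviews the blood count from each visit. An abnormal laboratory finding counts as an adverse event, and the physician reviews every adverse event (section 7, adverse event monitoring).
- Medication is discontinued in low-dose aspirin users if bruising or bleeding increases (section 7, risks associated with curcumin).
- Medication is stopped for "Development of medical problems listed as exclusion criteria". Those criteria include chronic gastrointestinal blood loss and iron deficiency.
- Grade 3 or 4 symptoms that limit continuation are a stop.

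On mechanism, section 7 says: "Curcumin may chelate iron and reduce its absorption. Serum ferritin will be checked at screening".

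**The concern.** A rule that compares each value with the one before it detects a sudden drop well and a gradual one poorly. Reduced iron absorption, which the protocol itself raises, would be expected to act gradually. Participants are 70 or older with some functional impairment, low-dose aspirin is allowed, and the study draws blood repeatedly. As written, a participant who loses 1.1 g/dL in one month must stop. One who loses 1.2 g/dL over two months need not, and at Month 2 may be given the final third of the treatment. Whether that participant stops is then left to judgement, symptoms or a diagnosis.

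**Working it through.** **Inputs from the protocol.** The threshold is a fall of more than 1 g/dL from the previous visit (section 7). Blood counts are taken at Baseline and at monthly visits (Enrollment and Randomization; Outcome Measures, Safety). About 60 mL of blood is drawn at Baseline and 30 mL at each monthly visit. The protocol gives no hemoglobin calculation to reproduce.

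**Assumed, not in the documents.** A steady true loss of r g/dL per month; independent normal within-person variation with SD 0.2 to 0.5 g/dL.

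**Step 1: where the two rules differ.** At Month 1 the previous visit is Baseline, so the rules coincide. At Month 3 dosing is over. That leaves the Month 2 decision.

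**Step 2: no measurement noise.** The values are H, H - r and H - 2r.

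- Written rule: triggers only if r > 1.0.
- With Baseline added: triggers by Month 2 if 2r > 1, that is r > 0.5.
- Any r above 0.5 and up to 1.0 therefore passes the written rule and fails the amended one. The largest untriggered loss at Month 2 is 2 x 1.0 = 2.0 g/dL.
- Example: from an illustrative start of 13.0 (it cancels out), r = 0.6 gives 13.0, 12.4, 11.8. Each fall is 0.6, so nothing triggers, yet the total is 1.2.

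Table 2, as extracted, also marks blood counts at Weeks 2, 6 and 10. The layout is flattened and the text says monthly, so the monthly reading is used. If those extra bloods are taken, the reference resets more often and the written rule becomes looser: 0.3 g/dL per visit never triggers, although the total is 1.2 at the fourth post-Baseline visit.

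**Step 3: with noise.** Let e0, e1, e2 be the errors at Baseline, Month 1 and Month 2. The written rule stops if r + e0 - e1 > 1 or r + e1 - e2 > 1. The amended rule also stops if 2r + e0 - e2 > 1. Share stopped by Month 2, from 1,000,000 simulated participants per cell, at SD 0.2 / 0.3 / 0.4 / 0.5:

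| True loss per month | Written rule | With *or from Baseline* |
|---|---|---|
| 0 | 0.000 / 0.018 / 0.077 / 0.157 | 0.001 / 0.025 / 0.099 / 0.190 |
| 0.4 (0.8 by Month 2) | 0.034 / 0.157 / 0.287 / 0.389 | 0.250 / 0.367 / 0.453 / 0.516 |
| 0.6 (1.2) | 0.157 / 0.342 / 0.465 / 0.544 | 0.765 / 0.711 / 0.702 / 0.706 |
| 0.8 (1.6) | 0.465 / 0.598 / 0.663 / 0.701 | 0.983 / 0.930 / 0.885 / 0.856 |
| 1.0 (2.0) | 0.833 at every SD | 1.000 / 0.992 / 0.970 / 0.944 |

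Rounding results to 0.1 g/dL changes little: at 0.6 per month, 11-51% versus 67-71%.

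**Step 4: false stops with no true loss.** At SD 0.5 the difference is 0.190 - 0.157 = 0.033. That is 24 x 0.033 = 0.8 participants, or 30 x 0.033 = 1.0. Both totals are shown because the Design section says 24 and the Statistical Analyses section says 15 per group. At SD 0.2 the difference is close to zero.

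**Step 5: false stops if blood draws lower hemoglobin.** Between the Baseline and Month 2 values the study draws 60 + 30 = 90 mL. Assume a blood volume of 4 to 5 L, hemoglobin of 12 to 14 g/dL and no replacement. The fall is then between 90/5000 x 12 = 0.22 and 90/4000 x 14 = 0.32 g/dL. At SD 0.5, stops go from 21-23% to 26-30%, which is 1.3 to 1.5 extra in 24 or 1.6 to 1.9 in 30, in either arm. At SD 0.2 the effect is negligible. No replacement is an extreme assumption, so this is an upper bound for that mechanism.

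**The case against.** The strongest reply is that 1 g/dL is a per-visit limit, and the sponsor never set a cumulative one. A reader might infer that the plan lets participants breach its own limit. The documents do not support that: applying 1 g/dL from Baseline is the reviewer's extension. The creatinine entry shows a different choice for a different analyte, not a contradiction. It does show that a Baseline reference is already workable in the same list.

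Second, the gap is narrow and watched. It is one decision about one month's supply in 24 to 30 people, and one physician sees every blood count. Abnormal laboratory findings count as adverse events without symptoms, and aspirin users have their own stop for bruising or bleeding. All of this stands. None of these provisions, however, puts a number on a cumulative fall. Ferritin is scheduled only at screening, so a stop for new iron deficiency has no planned test behind it.

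Third, no section shows that losses of 0.6 to 1.0 g/dL per month are likely. Section 7 calls the clinical implications of the interaction findings largely unknown and the bleeding risk theoretical. Bleeding disorders and iron deficiency are already excluded. Study blood draws explain only about 0.2 to 0.3 g/dL in total. This stands, and it is why the simulated rates are labelled as assumptions.

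Fourth, the gain depends on the SD. At 0.6 g/dL per month it is 61 percentage points at SD 0.2 (0.765 - 0.157) but 16 at SD 0.5 (0.706 - 0.544). This also stands, although the gain is positive throughout the range.

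**Conclusion.** The point holds as a minor safety refinement. The written rule allows falls of 1.0 g/dL or less per visit to add up to as much as 2.0 g/dL at Month 2 without a mandatory stop. That follows from the wording and the monthly schedule alone. The stopping rates also assume steady loss and independent error with SD 0.2 to 0.5 g/dL.

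A reader might infer that slow falls would go unnoticed, or that curcumin is expected to cause them. Neither is supported. Physician review, the other stops and measurement noise would catch some of these participants: even under the written rule, 16-54% are stopped by Month 2 at 0.6 g/dL per month. The documents give no rate of hemoglobin loss on curcumin.

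**What to change.** In the section 7 list, after "Decrease in hemoglobin of > 1 g/dL from previous visit" add *or from Baseline*, for all participants. Keeping the previous-visit comparison preserves detection of a sharp drop that follows a rise at Month 1.

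No new visit, draw or assay is needed, because the blood count is already taken at Baseline and monthly. The cost is extra stops. With no true loss these number 0 to about 0.8 in 24 participants (1.0 in 30), or up to about 1.5 in 24 (1.9 in 30) under the blood-draw assumption above. Some participants whose true loss is only 0.8 g/dL by Month 2 would also be stopped: 25-52% rather than 3-39%.
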